3.2 Analysis populations

We define the following patient population in this trial:

- Intention- to- treat analysis set: All patients that have been randomized will be analyzed according to the group they were originally assigned, regardless what treatment (or not) they received.
- Per protocol analysis set: All patients that were randomized, received treatment according to protocol without deviations (as described for in "compliance of

interventions" and "timing of follow-up visits" above) were analyzed according to the treatment they were randomized to.

3.3 Statistical Framework

Superiority hypothesis testing will be performed to test the effectiveness of the interventions compared to usual care, according to the null hypothesis as stated above. Superiority of rESWT group, sham-rESWT group or exercise group over usual care will be claimed if the two-sided p value in the test comparing the change from baseline to 6 months in NRS score is less than 5 %. This protocol is designed to address a single primary endpoint; measure of heel pain using NRS. A difference in the effect of the interventions will be claimed if null hypothesis is rejected, that is if the two-sided p- value is less than 5%.

3.4 Statistical interim analyses and stopping guidance

There will be no interim analyses in this trial.

If severe medical events occur, the manager of the department have access to unblind that particular patient.

3.5 Timing of final analysis

The analysis is timing stratified by planned length of follow-up. When all patients have completed a minimum of 6 months follow- up the analysis of the primary outcome will be performed. When all patients have completed a minimum of 12 months follow-up the secondary analysis will be performed.

3.6 Baseline patient characteristics

Baseline characteristics of the study population will be summarized separately with each randomized group. For continuous variables, means and standard deviations will be presented, unless the variable has a highly skewed distribution, in which case, medians 25th and 75th percentiles will be presented. For categorical (binary or ordinal) variables, the number and percentage of participants within each category will be presented. For each variable (continuous or categorical), the percentage of missing values will be reported.

4.0 Analysis methods

4.1 Statistical methods

The results of the trial will be presented following the standard CONSORT recommendations (7).

A CONSORT diagram will be used to show patient flow with number of patients considered and total numbers randomized.

All calculated p-values will be two-sided and compared to a 5% significance level. If a p-value is less than 0.05, the null hypothesis in the test will be rejected. Efficacy estimates for the comparison of treatment interventions will be presented with two-sided 95% confidence intervals.

P-values will be rounded to three decimal places. P-values less than 0.001 will be reported as <0.001 in tables. There will be no adjustment to secondary outcomes for multiple testing.

4.1.1 Analysis of primary outcome

The primary outcome is change in heel pain score (NRS) during activity last week from baseline to 6 months, will be analyzed using linear mixed effects model. The model will include fixed effects for time, and treatment x time interaction. The main effect of treatment group will be removed from the model to adjust for potential differences in the score at baseline. A random intercept will be used. Based on this model, the primary efficiacy outcome of between-group differences in changes from baseline to 6 months follow-up will be estimated. This model allows for comparison between rESWT, sham-rESWT and a standardised exercise programme compared to usual care. The primary effect analysis will use the intention- to treat population.

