2.0 Study methods

2.1 Trial design

The study is designed as a double- blind, randomized, sham-controlled trial, with four parallel groups.

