2.2 Randomization

Eligible patients were randomized in a 1:1 ratio. Treatment allocation was done by a computer generation randomization schedule with blocks of 8.

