4.1.2 Analysis of secondary outcomes

For secondary outcomes, assessed at multiple time points (baseline, 3, 6 and 12 months) will be analysed by using a linear mixed effect model approach as described in section 4.1.1 on both the intention-to treat population and the per protocol population

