4.5 Statistical software

All statistical analysis will be done using SPSS version 28 or STATA version 17.

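### Does removing the treatment main effect from the primary mixed model fail to adjust for baseline?

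*SAP*

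**What the plan says.** SAP section 4.1.1 describes the primary model in a few sentences. On the fixed effects: "The model will include fixed effects for time, and treatment x time interaction". On the treatment term: "The main effect of treatment group will be removed from the model to adjust for potential differences in the score at baseline". On the random part: "A random intercept will be used". On what is taken from the fit: "between-group differences in changes from baseline to 6 months follow-up will be estimated".

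The setting is a "randomized, sham-controlled trial, with four parallel groups" (section 2.1) with equal allocation ("Eligible patients were randomized in a 1:1 ratio", section 2.2). The schedule in section 2.4.2 has the pain score at baseline, 3, 6 and 12 months. Section 4.1.2 applies the same model to secondary outcomes "assessed at multiple time points (baseline, 3, 6 and 12 months"). Section 4.5 names the software: "All statistical analysis will be done using SPSS version 28 or STATA version 17".

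The SAP does not say in words that visit is categorical, or how the interaction columns are built.

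**The concern.** A two-way interaction between categorical factors can absorb a missing main effect. Suppose visit and treatment are both factors and the interaction has a group term at every visit, baseline included. Deleting the treatment main effect then changes only the labels of the parameters. Each arm keeps its own baseline mean and the fit equals that of the full factorial model. The contrast of changes would be the plain change-score difference, and the 6-month interaction coefficient read alone would be the raw 6-month difference. Neither is adjusted for baseline.

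Entering time as a number does not rescue the model on this view. The baseline means are then shared, but the group difference must grow in a straight line from zero, which would distort the 6-month estimate if the effect appears early and stays flat.

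At stake is the primary estimate: its precision, its response to chance baseline imbalance, and whether the SAP describes it correctly.

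**Working it through.** **Inputs from the SAP.** Four arms (section 2.1); visits at 0, 3, 6 and 12 months (section 2.4.2); difference 2, SD 2.7, two-sided 5%, power 90%, dropout 20%, 50 per group and 200 in total (section 2.3). The SAP gives no within-patient correlation *r*, so *r* is assumed over a range. The SD of 2.7 is taken as that of the score at a single visit.

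**The plan's own figure.** A two-sided t test for difference 2 and SD 2.7 at 90% power needs 39.3, so 40 per arm. Then 40/(1 - 0.2) = 50 per arm, and 4 × 50 = 200, as stated. This supplies the inputs below but does not decide the point.

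**Step 1: what the main effect is.** Take usual care and baseline as reference levels. The mean for arm *j* at visit *k* is

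μ(*j*,*k*) = β0 + β(*k*) + γ(*j*) + δ(*j*,*k*), with β and δ equal to zero at baseline.

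At baseline, arm *j* minus usual care is γ(*j*). The treatment main effect therefore is the baseline group difference, and removing it sets all arms to the common baseline mean β0.

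**Step 2: count the parameters (confirmed by matrix rank).**

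| Coding | Parameters |
|---|---|
| (a) Time + treatment + interaction | 1 + 3 + 3 + 9 = 16 |
| (b) No main effect, group terms at all four visits including baseline | 1 + 3 + 12 = 16 |
| (c) No main effect, group terms at 3, 6 and 12 months | 1 + 3 + 9 = 13 |

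Removing the main effect from (a) gives (c), three parameters fewer. Model (b) arises only when three baseline group terms are put back; it spans the same space as (a). If the 6-month analysis uses only baseline, 3 and 6 months, the counts are 12, 12 and 9, and the conclusion is the same.

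**Step 3: does (c) adjust?** Assume complete data, 50 per arm, a true 6-month effect of -2, and a chance baseline imbalance of 1 point that carries over to follow-up as *r* × 1.

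- (a) and (b), contrast of changes: (-2 + *r*) - 1.
- (c): (-2 + *r*) - *r* × 1 = -2.
- SE for (a) and (b): 2.7 × √[(2/50) × 2(1 - *r*)].
- SE for (c): 2.7 × √[(2/50) × (1 - *r*²)].

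| *r* | (a), (b): estimate (SE) | (c): estimate (SE) |
|---|---|---|
| 0.3 | -2.7 (0.639) | -2.0 (0.515) |
| 0.5 | -2.5 (0.540) | -2.0 (0.468) |
| 0.7 | -2.3 (0.418) | -2.0 (0.386) |

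Model (c) removes the imbalance and is the more precise.

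**Step 4: fit to simulated data** (*r* = 0.5). The maximised log-likelihood is -1797.607 for both (a) and (b), and -1798.654 for (c). The 6-month estimates are -2.229 (SE 0.537) and -2.035 (SE 0.460). Model (c) is a different model.

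**Step 5: the other two readings.**

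- *Raw 6-month difference.* The SAP asks for differences in change. Reporting the raw coefficient from (b) would contradict that sentence. In (c) the baseline mean is common, so the 6-month coefficient is itself the difference in change.
- *Linear time.* With months as a number, a flat effect of 2 at 3, 6 and 12 months would be estimated at 6 months as 1.18 for *r* = 0.2 and 0.95 for *r* = 0.6. But the SAP nowhere makes time linear, it lists discrete visits, and it wants a contrast at one of them. The flat profile is also an assumption.

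**The case for a change.** The strongest reply is that coding (c) is not written in the SAP either. Section 4.1.1 names terms, not columns. Given those terms as two factors, a formula parser can return (b): a Python one did, with rank 16. SPSS and Stata, the packages in section 4.5, were not tested. An analyst who types the terms without checking the columns could lose the adjustment.

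The cost would be real. The SE ratio is √[2/(1 + *r*)], which gives 1.29, 1.20 and 1.12 at *r* = 0.2, 0.4 and 0.6, so the change contrast has an SE 29%, 20% or 12% larger. With 40 per arm, power is about 79% against 93% at *r* = 0.3, and 90.5% against 96.5% at *r* = 0.5.

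The algebra stands for that coding. It does not show an error in the plan. The SAP says why the term is removed, and among the categorical codings only (c) serves that purpose; choosing (b) means putting back the baseline differences the SAP says it takes out. Even under (b), the contrast the SAP names is unbiased over repeated randomisation. The loss is of precision, and at *r* = 0.5 power still meets the planned 90%.

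**Conclusion.** The concern does not hold. Read with its stated purpose, section 4.1.1 describes the longitudinal model with a common baseline mean. Removing the main effect takes out three parameters (16 to 13), and the baseline adjustment follows. Random allocation justifies the constraint, because the arms have equal baseline means in expectation.

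This rests on visit being categorical with baseline as reference, and on group terms entering only at follow-up visits. The SAP does not spell these out, but they follow from the discrete visits, the 6-month contrast and the reason given for dropping the term. The numerical illustrations also assume complete data, equal variances and a constant within-patient correlation. The parameter count needs none of these. What is left is a programming check that no baseline group term has come back in, not a fault in the analysis plan.

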2.3 Sample size

The sample size was based on the primary outcome measure Numeric Rating Scale (NRS) at 6 months, for a comparison between two of the treatment groups using a two-sided t test. With a statistical test power of 90%, a significance level of 5 %, an assumed difference of 2 of NRS (2), estimated standard deviation (SD) of 2.7 (based on previous clinical data from the Department of Physical Medicine and Rehabilitation) and a dropout of 20%, the sample size was estimated to be 200, with 50 in each group.

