2.5 Timing of outcome assessments

1)Baseline variables: age, sex, relationship status, education, work situation, sick leave, duration of symptoms, previous treatment, previous use of radial extracorporeal shock wave treatment, use of pain medication, physical activity, smoke/non-smoker, expectation of change in foot pain, which treatment he/she hopes to get in the trial. In addition the physician register sick leave status and if the sick leave is because of foot pain. 2) NRS: Numeric Rating Scale. 3)FFI-RS: Foot Function Index revised short form. 4) RAND-12: RAND-12 Health Status Inventory.5)PGIC: Patient Global Impression of Change. 6) Other variables: Use of foot orthosis, side effects of treatment, use of other treatment modalities, use of pain medication. 7) Clinical examination includes palpation of the ankle and foot including the insertion of the

plantar fascia, weight-bearing ankle dorsiflexion motion, calf-raise test, measurement of calf circumference. In addition and only at inclusion: Measure of height, weight, body mass index, measure of passive range of motion in the ankle joint.

The ultrasound measures include thickness in millimeter, hypo echogenicity (presence/no presence), neovascularization (presence/no presence) and calcification (presence/no presence).

At baseline the patients completed the patient- reported outcome measures (PROMs): Numeric Rating Scale (NRS) (primary endpoint), RAND-12 Health status inventory (RAND-12) and Foot Function Index revised short form (FFI-RS) (secondary outcomes). In addition they completed a questionnaire including patient characteristics, anthropometric data and the duration of symptoms.

After 3 months, the patients received a letter with the same PROMs and in addition the Patients'Global Impression of Change Scalge (PGIC), which they filled out and returned. In addition they filled out a questionnaire regarding use of foot orthosis, side effects of treatment, use of other treatment modalities, and use of pain medication.

The patients were asked to complete the same PROMs and questionnaire as stated above prior to clinical examination and ultrasound at the 6- and 12 months follow-up visit.

At baseline, 6 months and 12 months follow-up the patients had a clinical examination including ultrasound.

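### The primary model's random intercept forces one variance and one correlation on baseline and follow-up, so the 6-month standard error can be wrong in either direction; an unstructured covariance over stated visits removes this.

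*SAP*

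**What the plan says.** SAP section 4.1.1 defines the primary outcome as change in NRS pain in activity "from baseline to 6 months, will be analyzed using linear mixed effects model". On the fixed part it says: "The model will include fixed effects for time, and treatment x time interaction". It continues: "The main effect of treatment group will be removed from the model to adjust for potential differences in the score at baseline". Baseline NRS is therefore one of the modelled responses, with a mean common to the four arms.

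On the covariance the section says only: "A random intercept will be used". No other section adds a residual structure, visit-specific variances, robust standard errors or a degrees-of-freedom method. Section 4.1.2 carries the same model to the secondary outcomes, which "will be analysed by using a linear mixed effect model approach as described in section 4.1.1".

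The visits in the primary model are not listed. Section 4.1.1 names baseline and 6 months. NRS is also collected at 3 months (section 2.5: "After 3 months, the patients received a letter with the same PROMs") and at 12 months (schedule in section 2.4.2). Section 3.5 sets the timing: "When all patients have completed a minimum of 6 months follow- up the analysis of the primary outcome will be performed". By then some patients may already have 12-month data. The only information on variability is in section 2.3: an "estimated standard deviation (SD) of 2.7".

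**The concern.** A random intercept with independent, homoscedastic residuals is compound symmetry: the same variance at every modelled visit and the same correlation between every pair. Baseline is measured before treatment and follow-up after four different treatments, so equality should not be assumed without support.

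In this model the 6-month contrast is the difference in 6-month means, less an estimated correlation times the difference in baseline means. Its reported standard error uses a variance averaged over visits rather than the 6-month variance. Other things equal:

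- It is too small if follow-up scores vary more than baseline scores, and too large if they vary less.
- With three or more visits, it is also too small if baseline correlates less with follow-up than the follow-up visits do with one another, and too large in the reverse case.

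This model supplies the p-value and 95% interval for all three primary comparisons, each judged at 5% (sections 3.3 and 4.1). Complete data would not cure the error.

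**Working it through.** **Inputs from the SAP.** Difference 2, SD 2.7, two-sided 5%, power 90%, dropout 20%, 50 per arm, four arms (section 2.3). **Assumed, because the SAP gives none:** SDs by visit and correlations between visits.

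**The plan's own figure.** An exact two-sample t calculation for a difference of 2 and SD 2.7 gives 40 per arm (power 90.5%). Then 40/0.8 = 50 per arm and 4 × 50 = 200. The sample size reproduces and is not in question. I use n = 40 evaluable per arm below.

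**Large-sample formula (complete data).** Let s² be the mean of the visit variances, c the mean of the pairwise covariances and ρ = c/s². V₀₀ and V₆₆ are the true variances at baseline and 6 months, and V₀₆ their covariance.

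- Variance the model reports: (2/n) · s² · (1 − ρ²)
- True variance of the same estimate: (2/n) · (V₆₆ − 2ρV₀₆ + ρ²V₀₀)
- Actual level: 2Φ(−1.96 · √(reported/true))

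**Worked example.** Two visits, SD 2.2 at baseline and 2.7 at 6 months, correlation 0.4:

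- s² = (4.84 + 7.29)/2 = 6.065; c = 0.4 × 2.2 × 2.7 = 2.376; ρ = 0.3918
- Reported: 0.05 × 6.065 × (1 − 0.1535) = 0.2567, SE 0.507
- True: 0.05 × (7.29 − 2 × 0.3918 × 2.376 + 0.1535 × 4.84) = 0.3086, SE 0.555
- SE ratio 0.912; actual level 2Φ(−1.788) = 7.4%

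**Actual level of the nominal 5% test, by formula.** "r b/f" is the correlation of baseline with follow-up, then of follow-up visits with each other; with two visits only the first applies.

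| SD at baseline, then follow-up; r b/f | 2 visits | 3 visits | 4 visits |
|---|---|---|---|
| 2.7, 2.7; 0.5/0.5 (assumption true) | 5.0% | 5.0% | 5.0% |
| 2.5, 2.7; 0.5/0.5 | 5.9% | 5.6% | 5.4% |
| 2.5, 2.7; 0.45/0.55 | 5.9% | 6.1% | 6.2% |
| 2.2, 2.7; 0.5/0.5 | 7.4% | 6.5% | 6.1% |
| 2.7, 2.7; 0.3/0.6 | 5.0% | 6.1% | 7.0% |
| 2.2, 2.7; 0.3/0.6 | 7.4% | 7.7% | 8.2% |
| 1.8, 2.7; 0.4/0.7 | 9.6% | 9.6% | 10.1% |
| 2.7, 2.4; 0.5/0.5 | 3.7% | 4.1% | 4.3% |
| 2.2, 2.7; 0.7/0.5 | 7.4% | 5.0% | 4.2% |

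With two visits and equal SDs the SE ratio is exactly 1 whatever the correlation. With three or four visits, unequal correlations matter even at equal SDs. That is why the visits must be stated.

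**Simulation under no effect.** 50 per arm, 20% completely random dropout, 4,000 runs, three contrasts per run, Monte Carlo error about 0.3 points. Three visits, per-comparison type I error:

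| SD; r b/f | Random intercept | Unstructured, Kenward–Roger |
|---|---|---|
| Common SD; 0.5/0.5 | 5.5% | 5.3% |
| 2.2, 2.7; 0.5/0.5 | 7.0% | 5.3% |
| Equal SDs; 0.3/0.6 | 6.0% | 5.1% |
| 2.2, 2.7; 0.3/0.6 | 7.6% | 5.1% |
| 1.8, 2.7; 0.4/0.7 | 9.6% | 4.9% |
| 2.7, then 2.4 | 4.3% | 5.3% |

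In the fifth row the mean reported SE was 0.464 against a true 0.546. With two visits the random intercept gave 7.7% (SD 2.2 then 2.7), 10.2% (1.8 then 2.7) and 3.7% (2.7 then 2.4). A separate, smaller two-visit simulation (400 trials per scenario, correlation 0.4, 6-month SD 2.7) gave 10.5% for baseline SD 1.8 and 2.5% for baseline SD 3.2. The four-visit figures are from the formula only.

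**Power after the change.** Under the correct unstructured covariance the SE is √[(2/40) × 7.29 × (1 − r²)], where r is the correlation of baseline with 6 months. For r = 0.3 it is 0.576, and power for 2 points is Φ(2/0.576 − 1.96) = 93.5%. For r = 0.2 it is 0.592 and power is 92.2%.

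**The case against.** The model in section 4.1.1 is coherent, contradicts nothing else in the SAP, and is valid if its assumption holds. The SAP gives no SD or correlation by visit, so neither the presence nor the direction of an error can be shown. This stands, and it is why no single error rate is claimed.

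Section 4.1.1 does not exclude heterogeneous residuals or robust standard errors. That is true, but an analyst who follows the text will fit the default random-intercept model, and no other section says otherwise.

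The larger figures come from large departures: SD 2.2 to 2.7 is a 51% rise in variance, and 1.8 to 2.7 a 125% rise. Milder departures give about 5.4–6.2%, and opposing departures can cancel, as the last row of the formula table shows for three visits. The simulated rates also carry some small-sample excess: 5.5% where the assumption is true, and 7.0% where the formula gives 6.5%. These points shrink the likely size but do not remove the problem.

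Other remedies exist. With two visits, separate residual variances would suffice, and robust standard errors largely work. An unstructured covariance is preferred because it covers every visit set at little cost, not because it is the only valid choice. Finally, the error matters mainly for borderline results; that too is fair.

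**Conclusion.** The concern holds. Followed as written, the primary model assumes equal variance and equal correlation across baseline and follow-up, with nothing in the SAP to support it, and its 5% tests and 95% intervals depend on that assumption. Under assumed covariances the per-comparison level is roughly 5.4–6.2% for mild departures, 6–8% for one moderate departure, and 8–10% for departures in both variance and correlation or a large SD gap. It is about 3–4% when baseline varies more than follow-up, and 5% if the assumption is true. These figures are illustrative, since only the SD of 2.7 comes from the SAP. No bias in the point estimate is claimed, and bias under outcome-dependent dropout was not examined. The change should be made before analysis. The case rests on the covariance; the unlisted visits add to it but would by themselves be only a missing detail.

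**What to change.** In section 4.1.1, list the visits that enter the primary model. Replace the random intercept with an unstructured residual covariance across those visits, fitted by REML with Kenward–Roger or Satterthwaite degrees of freedom, and keep the constrained baseline. Prespecify a fallback for non-convergence: the random intercept with cluster-robust standard errors, which gave 5.4–5.9% in the same simulations. Apply the same wording to the continuous secondary outcomes in section 4.1.2.

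The cost is two sentences and one changed model command, with no new data. Covariance parameters rise from 2 to 3, 6 or 10 for two, three or four visits, which is small for 200 patients. Confidence intervals may widen where the planned standard error would have been too small. Power for a 2-point difference with 40 evaluable per arm stays above 92% in the scenarios examined.

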4.1.2 Analysis of secondary outcomes

For secondary outcomes, assessed at multiple time points (baseline, 3, 6 and 12 months) will be analysed by using a linear mixed effect model approach as described in section 4.1.1 on both the intention-to treat population and the per protocol population

